#### A. Research Procedures

Procedure (in order of occurrence)	When	Where	By Whom
Recruitment of Participants Cross-sectional phase and interventional phase	May 2022-June 2024	various HIV treatment centers in the NJ region and/or HIV support groups	[name] [name] [name]  [name]
Screening for Eligibility Cross-sectional phase and interventional phase	May 2022–June 2024	By phone or HIPAA compliant ZOOM meeting	[name]  [name]
Consenting Cross-sectional phase and interventional phase	May 2022–June 2024	Rutgers study site (in Newark or Voorhees) or Wm Way Center in Philadelphia	[name]  [name]
Baseline Testing (Week 0) Cross-sectional phase and interventional phase	May 2022–June 2024	Rutgers study site (in Newark or Voorhees) or Wm Way Center in Philadelphia for in-person tests and questionnaires Physical activity monitoring done at home	[name] [name] [name]  [name]
Group assignment and instruction in interventions for TENS and MM groups Interventional phase only	May 2022–June 2024	Rutgers study site (in Newark or Voorhees) or Wm Way Center in Philadelphia	[name] [name]  [name]
Home-based Interventions and daily	May 2022–July 2024	Participant's home	Participant

question re: adherence via text message (6 weeks) Interventional phase only			
Post-intervention Testing (Week 7) Interventional phase only	May 2022–July 2024	Rutgers study site (in Newark or Voorhees) or Wm. Way Center in Philadelphia for in-person tests and questionnaires Physical activity monitoring done at home	[name] [name] [name]  [name]
Follow up Questionnaire (Week 15) Interventional Phase only for those who were in TENS or MM groups and enrolled after IRB approval to add follow up questionnaire.	April 2024 – Sept. 2024	Participant's home or location of choice via Email/RedCap	[name]

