## B. Data Points

Data elements include an array of non-invasive physical performance tests, physical activity monitoring, pain pressure threshold testing, and questionnaires. See Section 1.6 B. for detail on dependent variables/outcome measures.

The data elements will be collected at baseline (Week 0) for all participants.

At Week 0, all participants complete a demographic and health questionnaire and a physical activity questionnaire, the Brief Pain Inventory, and will undergo testing related to gait, walking endurance, physical performance, and pain-pressure threshold. They will receive a physical activity monitor that they will be asked to wear for 5 days and then ship back to the PI in a pre-paid shipping box.

Those with DSP-related pain will also complete questionnaires for pain, quality of life, depression and anxiety, catastrophizing behavior, and resilience at Week 0.

Those participants with DSP-related pain will be randomized to continue on to the interventional phase. Throughout the 6-week intervention period, participants in the TENS and MM groups will receive a daily text message in the morning that will ask them if they completed the home-based treatment on the day prior, and a weekly text message to ask if any problems have emerged; participants in the standard care group will receive a weekly text message to ask if any problems have emerged. All participants in the interventional phase will return for follow up testing after 6 weeks of intervention (Week 7), at which time all measurements taken at Week 0 will be repeated. In addition, participants will complete a satisfaction questionnaire at Week 7. They will once again receive a physical activity monitor that they will be asked to wear for 5 days and then ship back to the PI in a pre-paid shipping box. In addition, those who were randomized to the TENS or MM groups starting in March 2024 will complete a short follow up questionnaire at Week 15.

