#### 1.5 Sample Size Justification

A sample of 80 participants will be enrolled in the cross sectional phase and 40 participants (those with DSP) will continue on to the interventional phase.

The target sample size of 72 (36 with DSP and 36 without DSP) for the cross sectional phase is adequate to explore of between group differences in gait, physical performance, physical activity, and pain pressure threshold variables. For the interventional phase, 36 participants (12 participants in each of the 3 groups) is adequate to demonstrate feasibility and determine effect sizes that can inform a future randomized controlled trial. The expected accrual rate is 90% (drop-out rate of <10%); thus, the number enrolled will be 80.

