###### ▪ Process of Data Collection:

Data	How it will be collected	Who will oversee the process
Demographic and health information	Questionnaire (web-based using RedCap) Completed on-site	[name] [name] [name]  [name]
Zeno instrumented walkway with PKMAS gait analysis	On-site using portable equipment (Zeno	[name] [name]

software (Protokinetics Inc., Havertown, PA)	instrumented walkway) and laptop computer.	[name] [name]
6-Minute Walk Test	On-site using space in the lab or hallway that is clear.	[name] [name] [name]  [name]
Actigraph GT3X-BT device with ActiLife software (Actigraph, Pensacola, FL)	While on-site, participant will receive instruction in use of Actigraph device. After the participant receives instruction in use of the device, they will be wear it for 5 days, then ship it back to the PI in a pre-paid shipping box.  Data from the participant will be downloaded into a laptop computer before the device is wiped of date, disinfected, and prepared to use with a different participant.	[name]
International Physical Activity Questionnaire Short-Form (IPAQ-SF)	Questionnaire (web-based using RedCap) Completed on-site	[name] [name]  [name]  [name]
Short Physical Performance Battery	On-site, using portable equipment (chair, stopwatch)	[name] [name] [name]  [name]
Mid-thigh Pull	On-site, using portable equipment (load cell platform)	[name] [name] [name]  [name]
Digital Algometer (JTech Medical, Midvale, UT)	On-site, using portable digital algometer	[name] [name] [name]  [name]
Brief Pain Inventory	Questionnaire	[name]

	(web-based using RedCap) Completed on-site	[name] [name] [name]
Medical Outcomes Study HIV Health Survey (MOS-HIV)	Questionnaire (web-based using RedCap) Completed on-site	[name] [name] [name] [name]
Hospital Depression and Anxiety Scale (HADS)	Questionnaire (web-based using RedCap) Completed on-site	[name] [name] [name] [name]
Pain Catastrophizing Scale	Questionnaire (web-based using RedCap) Completed on-site	[name] [name] [name] [name]
Pain management questionnaire	Questionnaire (web-based using RedCap) Completed on-site	[name] [name] [name] [name]

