Brief Resilience Scale	Questionnaire (web-based using RedCap) Completed on-site	[name] [name] [name] [name]
Tracking of adherence to home-based treatment	Participant responses to daily text message from a study-specific Twilio account.	[name] [name]
Satisfaction questionnaire	Questionnaire (web-based using RedCap) Completed on-site	[name] [name] [name] [name]
Follow up questionnaire (for those who were in TENS and MM groups)	Questionnaire (web-based using RedCap) Completed at participant's home or location of their choice.	[name]

- **Timing and Frequency:**

Cross-sectional phase: All participants will be seen individually at Week 0 (baseline) for all variables included in the cross-sectional study. In addition, participants will wear an activity monitor for 5 days following the baseline session.

Interventional phase. Participants who continue on into the interventional phase (those with DSP) will complete additional questionnaires at Week 0 and then will be seen again at Week 7 (following 6 weeks of home-based intervention or usual care). In addition, participants will wear an activity monitor for 5 days following the Week 7 session.

At Week 0, the expected time to complete all data collection for those participants without DSP is 45 minutes (gait and physical performance tests) and the expected time for those participants with DSP is 1.5 hours (45 minutes for gait and physical performance tests and 45 minutes for questionnaires.)

At Week 7, the expected time to complete all data collection is 1.5 hours (45 minutes for gait and physical performance tests and 45 minutes for questionnaires.)

At week 15, participants who were randomized to the TENS and MM groups will receive a short follow-up questionnaire (5-10 minutes to complete)

- **Procedures for Audio/Visual Recording:** Not applicable.

- **Study Instruments:**

Instrument	Details	References to support Validity and Reliability

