## 6.0 Data Management Plan

### 6.1 Data Analysis

Cross-sectional phase: We will test for baseline differences between those with painful DSP and those without painful DSP for the set of variables using independent t-tests (or Mann-Whitney tests if distributions are non-normal). Differences between those with and without DSP on potential demographic or clinical confounders will be adjusted for statistically.

Interventional phase: Assuming normality of the outcome variables of interest, between group repeated measures analysis of variance will be used to evaluate differences within and between groups for each outcome separately. In the case of non-normal outcome variable distribution, we will consider transforming the measure to normalize. If normalization is not warranted, then within group changes will be tested using a Friedman's test and between group differences will be compared descriptively. Data will be analyzed using both per-protocol and intention-to-treat analyses in the case of dropouts.

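### Participants who miss the Week 7 visit cannot give any Week 7 outcome, although the questionnaires are web forms, so for them the intention-to-treat analysis reduces to attenders

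*Combined protocol and SAP*

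**What the plan says.** - **Analysis.** For the interventional phase, Section 6.1 states that "between group repeated measures analysis of variance will be used to evaluate differences within and between groups for each outcome separately". On analysis sets it adds: "Data will be analyzed using both per-protocol and intention-to-treat analyses in the case of dropouts". It defines neither set and names no method for missing Week 7 values.
- **Timing.** Sections 1.3 B and 1.6 B place the effect outcomes at Week 0 and Week 7 only. Week 15 covers ongoing use of the intervention, and only in the TENS and MM groups.
- **Who is due at Week 7.** Section 1.3 B: "All participants in the interventional phase will return for follow up testing after 6 weeks of intervention (Week 7". Continuing the home treatment is not a stated condition.
- **Where Week 7 data are collected.** The Section 1.3 A table gives the study sites, ending "in Philadelphia for in-person tests and questionnaires Physical activity monitoring done at home". In Section 1.9 the IPAQ-SF, Brief Pain Inventory, MOS-HIV, HADS, Pain Catastrophizing Scale, pain management, Brief Resilience Scale and satisfaction forms are all RedCap forms to be filled in at the site; the typical entry reads "Questionnaire (web-based using RedCap) Completed on-site".
- **A remote form already exists.** For the Week 15 RedCap questionnaire, Section 1.9 says: "Completed at participant's home or location of their choice".
- **Expected loss.** Section 1.5: "The expected accrual rate is 90% (drop-out rate of <10%); thus, the number enrolled will be 80".

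**The concern.** The plan expects some participants not to finish and promises an intention-to-treat analysis because of them. Yet its collection rules leave someone who does not attend Week 7 with no way of supplying pain, quality of life, mood, catastrophizing, resilience or satisfaction data. Gait, walking, strength and algometry need a visit. Nothing in the documents says that a web questionnaire does.

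What is at stake is selective loss. People who found an intervention unhelpful or burdensome may be less likely to travel back, and their absence would make the effect estimates look better than they are. Sections 1.4 and 1.5 name feasibility and effect sizes for a future trial as the purpose of this phase. Satisfaction is asked only at Week 7, so the same people's opinions would be lost too.

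**Working it through.** **1. The plan's own figures.** Inputs from Section 1.5: 72 completers overall, 36 in the interventional phase (12 per arm), dropout below 10%.

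- Enrolment = completers / (1 − dropout): 72 / 0.90 = 80 and 36 / 0.90 = 40. Both stated totals are reproduced.
- Loss allowed for in the interventional phase: 40 − 36 = 4, or 40 × 0.10 = 4. Since the stated rate is below 10%, 4 is the ceiling.

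**2. What a non-returner contributes.** With two time points, the standard repeated measures ANOVA needs both values from each person. The fallback in Section 6.1, Friedman's test, also needs both. No imputation or likelihood-based method is named. A person with only a Week 0 value therefore drops out of the comparison whichever analysis set is used.

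**3. Possible bias.** The documents give no SD or effect size, so this step is illustrative. Assume about 13 per arm (40 / 3 = 13.3), *k* people lost in one arm, none lost in the comparator, and a mean change among those lost that is δ SD worse than among those seen. If completers average μ, the full arm averages [(13 − k)μ + k(μ − δ)] / 13 = μ − (k/13)δ. The completers' mean is too favourable by (k/13)δ:

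| Lost in one arm | δ = 0.5 SD | δ = 1 SD |
|---|---|---|
| 1 of 13 | 0.04 SD | 0.08 SD |
| 2 of 13 | 0.08 SD | 0.15 SD |
| 4 of 13 | 0.15 SD | 0.31 SD |

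The last row puts the whole planned loss in one arm. Equal loss with equal δ in both arms would cancel. Loss in the comparator alone would reverse the sign.

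**4. Precision.** The half-width of a two-arm 95% confidence interval, in SD units, is t(0.975, 2m − 2) × √(2/m), with *m* per arm. The two-sided 95% level is an assumption.

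- 36 with Week 7 data (m = 12): 0.85 SD.
- 38, if 2 of the 4 answer remotely (m = 12.67): 0.82 SD.
- 40, if all 4 answer (m = 13.33): 0.80 SD.

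The gain in precision is small and applies to questionnaire outcomes only.

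**The case against.** The best reply is that the plan already brings people back. Section 1.3 B has everyone in the interventional phase return, whether or not they kept up treatment. Section 1.3 D mentions withdrawal only after a serious adverse event or by the participant's choice. Section 1.3 A withholds TENS from some people randomised to it without removing them from the study. This stands. A reader might infer that anyone who gives up TENS or meditation loses all Week 7 outcomes, but the documents do not support that: such a person is still due at Week 7 and supplies intention-to-treat data.

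Nor do the documents support saying that the intention-to-treat analysis has no data at all. Non-adherent attenders are included, non-returners have Week 0 values, and TENS and MM participants may also have text replies on adherence. A mixed model or imputation could use the baseline values under assumptions. However, the plan names no such method, and none would supply an observed Week 7 value.

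The plan also works to limit loss. Means to travel is an inclusion criterion (Section 4.1 C), several sites are offered, a second gift card and travel cash are paid at Week 7 (Section 4.6 B), and weekly texts keep contact. The effect is modest: the 0.15 SD scenario is under one-fifth of the 0.85 SD half-width (0.15 / 0.85 = 0.18).

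The Week 15 form is an imperfect precedent. It takes 5 to 10 minutes, against 45 minutes for the Week 7 questionnaires. Remote answers would also have to pass through the score-based advice in Section 4.7 D and the 24-hour review in Section 6.3 A. These points limit the gain and call for extra wording, but none gives a non-returner a route to answer.

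**Conclusion.** The point holds for participants who do not attend Week 7. As written, they can give no Week 7 outcome and are absent from the repeated measures comparison, so for them the promised intention-to-treat analysis reduces to attenders. By the plan's own rate this is at most about 4 of 40. The illustrative bias of 0.08 to 0.15 SD rests on 2 of 13 lost in one active arm, none in the comparator, and non-returners doing 0.5 to 1 SD worse. None of these assumptions comes from the documents. The case for change rests on selective loss and on a promise that cannot be carried out for these people, not on precision.

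On-site completion is only part of the cause. Tests that need a visit would stay missing whatever is done about the questionnaires. This is an inexpensive improvement worth making.

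**What to change.** - **Sections 1.3 B and 1.9.** State that participants in any of the three arms who stop the home treatment are still due at Week 7. State that anyone who does not attend, and has not withdrawn consent for data, is sent the Week 7 RedCap questionnaires by email or text in the same window. Offer reading by phone or ZOOM where the read-aloud accommodation in Section 4.1 C is needed.
- **Safety review.** State that the score review in Sections 4.7 D and 6.3 A applies equally to remote responses.
- **Data.** Record on-site or remote mode for each Week 7 questionnaire.
- **Section 6.1.** Analyse remote responders in their assigned arm for questionnaire outcomes. Define both analysis sets and say how values still missing are handled. Limit the intention-to-treat claim for gait, 6-minute walk, SPPB, mid-thigh pull and algometry, which stay missing for non-returners. Activity monitoring is also described with the visit and belongs in the same limitation unless a route for sending the device out is added.

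The cost is some protocol wording and reuse of means already in place: RedCap survey links (Section 6.2), participants' mobile phones (Section 4.1 C) and the study texting account (Section 1.9). About four participants are affected. The downsides are a mixed mode of administration that coincides with non-attendance, and non-response by some of those contacted.

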## 6.2 Data Security

All data will ultimately be stored in a password protected folder on the university servers and accessible only to appropriate project team members. Data will be linked only to participant study ID#s, i.e. key codes. The de-identified data file will be shared with [name] (co-investigator and statistician) and other co-investigators as needed for purposes of analysis. A separate secure spreadsheet that links participant ID#s to their names will be kept on a separate password protected folder on a university server available only to [name] (PI) and [name] (co-investigator) and will be accessed only if the code needs to be broken in order to contact a participant based on any measurements or questionnaire responses that suggest need for a referral for medical attention or counseling. Signed consent forms will be scanned into a separate secure password protected folder on the university servers and accessible only to appropriate project team members, after which paper copies will be shredded. [name] (PI) is responsible for assuring security of all de-identified data, the spreadsheet that links participant names to participant ID#s, and signed consent forms. Any co-investigators and study staff involved with data collection ([name], [name], [name]) will be trained by PI ([name]) in all security protocols.

Data will be entered into the RedCap platform and RedCap via survey links that are created for this study, and will later transferred to in a password protected folder on the university servers and accessible only to appropriate project team members.

ZENO walkway data will be stored and processed on a password protected laptop dedicated to the ZENO walkway. The laptop with ZENO walkway data will be continuously within the line of sight of [name] or [name] or [name] during data collection and securely stored during transport between data collection locations. ZENO walkway data will be transferred from the dedicated laptop to a secure password protected folder on the university servers. After processing ZENO walkway data with PKMAS gait analysis software, the raw and aggregate ZENO walkway data will be uploaded into the RedCap project.

Mid-thigh pull test data will be uploaded into the RedCap project.

Actigraph data will be transferred from the Actigraph device to a password protected folder on the university servers, after which Actigraph devices will be wiped of participant data and disinfected prior to the device being used by a subsequent participant. After processing Actigraph data with ActiLife software, the raw and aggregate Actigraph data will be uploaded into the RedCap project. Text messages and responses to text messages about adherence to interventions (TENS and MM groups only during the 6 weeks of home-based treatment) will be done through a study-specific password protected Twilio account, and then uploaded into the RedCap project.

## 6.3 Data and Safety Monitoring

### A. Data/Safety Monitoring Plan

This study does not pose greater than minimal risk of harm. However, during on-site testing, participants will be closely monitored and supervised to assure safety.

The PI will maintain a record of any concerns or problems reported by participants. If such concerns or problems are serious and/or an adverse event, they will be reported to the IRB.

The PI will review data on an ongoing basis after any baseline (W0) or post-intervention (W7) testing sessions. Participants in the interventional phase will be reminded weekly via text message (using a study specific password protected Twilio account) to contact the PI if they are experiencing any problems or difficulties or have questions. Post-intervention (W7) data will be reviewed by the PI

([name]) within 24 hours after the collection of data to assess if any data suggests that the participant was harmed.

#### **B. Data/Safety Monitoring Board Details**

Not applicable as this study does not pose greater than minimal risk of harm.

### **6.4 Reporting Results**

#### **A. Individual Subjects' Results**

Individual results will not be shared with participants. However, if participants have any test scores (such as abnormal vital signs or observed behavior that is suggestive of severe depression or suicidal ideation), they will be alerted of the finding by the PI ([name]) and advised to seek medical attention or counseling.

#### **B. Aggregate Results**

Study findings will be posted to ClinicalTrials.gov. Participants who wish to review aggregate results of the study will be directly to ClinicalTrials.gov.

#### **C. Professional Reporting**

Results of the study will be submitted for presentation in the form of a poster or platform at least one national or international conference such as the American Physical Therapy Association Combined Sections Meeting. It is anticipated that the study will yield at least 2 manuscripts that will be submitted to appropriate peer-reviewed journals such as *Physical Therapy* or *AIDS Care*.

#### **D. Clinical Trials Registration, Results Reporting and Consent Posting**

This study includes both an observational phase (cross-sectional phase) and a pilot clinical trial (interventional phase). It will be registered with ClinicalTrials.gov.

### **6.5 Secondary Use of the Data**

Not applicable. Data will not be shared with other researchers.

### **7.0 Research Repositories – Specimens and/or Data**

Not applicable.

### **8.0 Approvals/Authorizations**

Not applicable. Required Departmental Reviews for study personnel from Rutgers have been noted in Section 1.3 of the eIRB application.

